8.2.1 Procedures to be Followed in the Event of Abnormal Clinical Findings

If a physiologic parameter, e.g., vital signs, is outside of the protocol-specified range, then the measurement may be repeated once if, in the judgment of the participating site PI or appropriate sub-investigator, the abnormality is the result of an acute, short-term, rapidly reversible condition (e.g., stress, anxiety or “white coat syndrome”) or other source of error. A physiologic parameter may also be repeated if there is a technical problem with the measurement caused by malfunctioning, or an inappropriate measuring device (i.e., inappropriate-sized BP cuff).

All abnormal clinical findings that occur post vaccination will be considered AEs.

8.3 Adverse Events and Serious Adverse Events

8.3.1 Definition of Adverse Event (AE)

AE means any untoward medical occurrence associated with the use of an intervention in humans, whether or not considered intervention-related [21 CFR 312.32 (a)]. An AE can therefore be any unfavorable and unintended sign, symptom or disease temporally associated with the use of medicinal (investigational) product.

Any medical condition that is present at the time that the subject is screened will be considered as baseline and not reported as an AE. However, if the severity of any pre-existing medical condition increases, it should be recorded as an AE.

AEs can be further divided into solicited AEs and unsolicited AEs. Solicited AEs are those for which the study team will specifically query the subject whether they occurred. Unsolicited AEs are those events that the subject report occurring without being queried about the specific event.

All AEs will be assessed for severity and relationship to study intervention ([Section 8.3.4](#)). Reporting of all AEs, solicited and unsolicited, will occur during the period from study product administration on Day 1 through 28 days after each vaccination. After 28 days post last vaccination through the end of planned study participation, only SAEs, Protocol Specified AESIs, MAAEs, and NOCMCs will be reported as AEs.

All AEs, solicited and unsolicited, will be captured on the appropriate DCF. Solicited AEs will be regarded as related to the study product and will not require separate entry into the AE log. Information to be collected for unsolicited AEs includes event description, date of onset, assessment of severity, relationship to study product and alternate etiology (assessed only by those with the training and authority to make a diagnosis and listed on the Form FDA 1572 as the participating site PI or appropriate sub-investigator), date of resolution, seriousness, and outcome. AEs occurring during the study-collection and reporting period will be documented appropriately regardless of relationship.

AEs will be followed to resolution or stabilization.

8.3.1.1 Solicited Adverse Events

Solicited AEs are anticipated local and systemic AEs for which consistent collection of information is desired. Study clinicians will follow and collect resolution information for any reactogenicity symptoms that are not resolved within 7 days.

Solicited AEs (i.e., reactogenicity) will be collected using a memory aid and recorded on the appropriate DCF from the time of each vaccination through 7 days post each vaccination.

For this study, solicited AEs will be:

- Injection site Pain
- Injection site Erythema
- Injection site Edema/Induration
- Headache
- Fatigue
- Myalgia
- Arthralgia
- Nausea
- Fever
- Chills

Subjects will also be assessed for delayed onset local reactions through 14 days post each vaccination.

8.3.1.2 Unsolicited Adverse Events

All AEs spontaneously reported by the subject and/or in response to an open question from study staff or revealed by observation, physical examination or other diagnostic procedures must be recorded on the appropriate DCF.

Unsolicited AEs of all severities will be reported from the time of study product administration through 28 days post each vaccination.

After 28 days post last vaccination through the end of planned study participation, only SAEs, AESIs, MAAEs, and NOCMCs (as detailed in [Section 8.3.9](#)) will be reported as AEs.

8.3.1.3 Special Reporting of Adverse Events

Not Applicable

8.3.2 Definition of Serious Adverse Event (SAE)

An SAE is defined in 21 CFR 312.32 as follows: “An AE or suspected adverse reaction is considered serious if, in the view of either the participating site PI or appropriate sub-investigator or the sponsor, it results in any of the following outcomes:

- Death,
- a life-threatening AE,
- inpatient hospitalization or prolongation of existing hospitalization,

- a persistent or significant incapacity or substantial disruption of the ability to conduct normal life functions,
- or a congenital anomaly/birth defect.

Important medical events that may not result in death, be life-threatening, or require hospitalization may be considered serious when, based upon appropriate medical judgment, they may jeopardize the patient or subject and may require medical or surgical intervention to prevent one of the outcomes listed in this definition. Examples of such medical events include allergic bronchospasm requiring intensive treatment in an emergency room or at home, blood dyscrasias or convulsions that do not result in inpatient hospitalization, or the development of drug dependency or drug abuse.”

“Life-threatening” refers to an AE that at occurrence represents an immediate risk of death to a subject. An event that may cause death if it occurs in a more severe form is not considered life-threatening. Similarly, a hospital admission for an elective procedure is not considered an SAE.

All SAEs, as with any AE, will be assessed for severity and relationship to study intervention.

All SAEs will be recorded on the appropriate SAE DCF.

All SAEs will be followed through resolution or stabilization by a study clinician, licensed to make medical diagnoses and listed on the Form FDA 1572 as the participating site PI or appropriate sub-investigator.

All SAEs will be reviewed and evaluated by DMID and will be sent to the SMC (for periodic review unless related) and IRB/IEC.

8.3.3 Suspected Unexpected Serious Adverse Reactions (SUSAR)

A SUSAR is any SAE where a causal relationship with the study product is at least reasonably possible but is not listed in the Investigator’s Brochure (IB), Package Insert, and/or Summary of Product Characteristics.

8.3.4 Classification of an Adverse Event

The determination of seriousness, severity and causality will be made by an on-site investigator who is qualified (licensed) to diagnose AE information, provide a medical evaluation of AEs and classify AEs based upon medical judgment. This includes, but is not limited to, physicians, physician assistants and nurse practitioners.

8.3.4.1 Severity of Adverse Events

All AEs and SAEs will be assessed for severity, according to the toxicity grading scales in the FDA “Toxicity Grading Scale for Healthy Adult and Adolescent Volunteers Enrolled in Preventive Vaccine Clinical Trials”.

For AEs not included in the protocol-defined grading system, the following guidelines will be used to describe severity.

Mild (Grade 1): Events that are usually transient and may require only minimal or no treatment or therapeutic intervention and generally do not interfere with the subject's usual activities of daily living.

Moderate (Grade 2): Events that are usually alleviated with additional specific therapeutic intervention. The event interferes with usual activities of daily living, causing discomfort but poses no significant or permanent risk of harm to the research subject.

Severe (Grade 3): Events interrupt usual activities of daily living, or significantly affects clinical status, or may require intensive therapeutic intervention. Severe events are usually incapacitating.

Potentially Life Threatening (Grade 4): Events that lead to an ER visit or hospitalization. (recorded on Adverse Event log as a Serious Adverse Event (SAE) and to be reviewed by Medical Monitor). Death (Grade 5): Events that lead to death (recorded on Adverse Event log as a Serious Adverse Event (SAE) and to be reviewed by Medical Monitor). AEs characterized as intermittent require documentation of onset and duration of each episode. The start and stop date of each reported AE will be recorded on the appropriate DCF. Changes in the severity of an AE will be documented to allow an assessment of the duration of the event at each level of intensity.

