8.3.7 Serious Adverse Event Reporting

8.3.7.1 Investigators Reporting of SAEs

Any AE that meets a protocol-defined criterion as an SAE must be submitted immediately (within 24 hours of site awareness) on an SAE form to the DMID Pharmacovigilance Group, at the following address:

DMID Pharmacovigilance Group
Clinical Research Operations and Management Support (CROMS)
[name]
[name]
SAE Hot Line: [name] (US) or [name] (outside US)
SAE [contact] (US) or [name] (outside US)
SAE Email Address: [contact]

In addition to the SAE form, select SAE data fields must also be entered into the SCHARP's EDC system. Refer to the protocol-specific MOP for details regarding this procedure.

Other supporting documentation of the event may be requested by the DMID Pharmacovigilance Group and should be provided as soon as possible. The DMID Medical Monitor will review and assess the SAE for regulatory reporting and potential impact on study subject safety and protocol conduct.

At any time after completion of the study, if the participating site PI or appropriate sub-investigator becomes aware of an SAE that is suspected to be related to study product, the participating site PI or appropriate sub-investigator will report the event to the DMID Pharmacovigilance Group.

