In the event of thrombocytopenia, study site personnel should report the absolute value for the platelet count and the reference range for the laboratory test used.

For either a thrombotic event or thrombocytopenia, testing for anti-PF4 should be performed at the local laboratory or substitute local laboratory; repeat testing may be requested for confirmation upon sponsor discretion.

- All suspected cases of myocarditis and pericarditis must be reported as AESI. Symptoms of chest pain, shortness of breath or palpitations may represent myocarditis or pericarditis. Typically, onset of symptoms has been within a few days following receipt of the mRNA COVID-19 vaccines.
- Guillain Barré Syndrome has occurred in some people who have received the Janssen COVID-19 Vaccine and will be recorded as an AESI in this study. In most circumstances, symptoms began within 42 days following receipt of dosing.

NOCMCs – defined as any new ICD diagnosis (per current International Statistical Classification of Diseases and Related Health Problems) that is applied to the subject during the course of the study, after receipt of the study agent, that is expected to continue for at least 3 months and requires continued health care intervention.

MAAEs – defined as a hospitalization, emergency room visit or an otherwise unscheduled visit to or from medical personnel for any reason; and considered related to study product.

All AESIs are assessed, recorded, and followed as described above under AEs. AESIs that meet SAE criteria will be reported on an SAE form within 24 hours to the DMID Pharmacovigilance Group, at the following address:

DMID Pharmacovigilance Group
Clinical Research Operations and Management Support (CROMS)
[name]
[name]
SAE Hot Line: [name] (US) or [name] (outside US)
SAE [contact] (US) or [name] (outside US)
SAE Email Address: [contact]

In addition, for documentation and medical assessment purposes AESIs that do not meet SAE criteria will also be reported on an SAE form and must be submitted immediately (within 24 hours of site awareness) to the DMID Pharmacovigilance Group; however, the narrative will indicate that the AESI did not meet SAE criteria.

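### For adverse events outside the FDA toxicity scale, Protocol 8.3.4.1 records an ER visit alone as an SAE, which 8.3.2 does not, so SAP Tables 50 and 59 can mix two definitions

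*Protocol*

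**What the plan says.** Protocol 8.3.4.1 refers first to the FDA toxicity grading scale. It then gives a fallback: "For AEs not included in the protocol-defined grading system, the following guidelines will be used to describe severity". In the fallback, Grade 4 (labelled potentially life-threatening) is "Events that lead to an ER visit or hospitalization. (recorded on Adverse Event log as a Serious Adverse Event (SAE", with review by the Medical Monitor.

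Protocol 8.3.2 defines an SAE by outcomes. The one that concerns hospital care is "inpatient hospitalization or prolongation of existing hospitalization". Events without a listed outcome "may be considered serious when, based upon appropriate medical judgment, they may jeopardize the patient or subject". On the life-threatening outcome it adds: "An event that may cause death if it occurs in a more severe form is not considered life-threatening".

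Protocol 8.3.4 says who decides: "The determination of seriousness, severity and causality will be made by an on-site investigator". Protocol 8.3.7.1 sets the clock: "Any AE that meets a protocol-defined criterion as an SAE must be submitted immediately (within 24 hours of site awareness". It does not say whether the criterion is the one in 8.3.2 or also the one in 8.3.4.1.

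Protocol 8.3.9 counts an emergency room visit considered related to study product as a medically attended event (MAAE), a category collected alongside SAEs but separate from them. It also has a route for special-interest events that are not serious: "AESIs that do not meet SAE criteria will also be reported on an SAE form and must be submitted immediately", with the narrative stating that SAE criteria were not met.

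SAP 9.4 summarizes SAEs in Table 59 and lists them in Table 60, which has a column for the reason each was reported as an SAE. Table 50 has rows for participants with any SAE and with any related SAE.

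**The concern.** A severity guideline attaches SAE status to a visit type, whereas the SAE definition rests on outcomes or judgment. Take an event off the FDA scale in a participant who is seen in an emergency room and sent home, with no immediate risk of death and no finding that it was an important medical event. Under 8.3.4.1 it is recorded as an SAE; under 8.3.2 it is not one. Two sites could classify the same event differently, each following the protocol's text.

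SAEs are part of the primary safety endpoint. What is at stake is how the SAE counts in Tables 50 and 59 read. Neither table shows how many events meet 8.3.2, so a reader who takes the SAE row in the usual sense may be looking at a mixture. In a group of 50, one participant is 1/50 = 2 percentage points.

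**Working it through.** **Do the two rules differ?** The claim about the text needs no arithmetic. Consider an off-scale event with an ER visit and no admission, and go through the ways in which it could be an SAE under 8.3.2.

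| Route to SAE status in 8.3.2 | Does an ER visit alone satisfy it? |
|---|---|
| Death, incapacity, congenital anomaly | No |
| Inpatient hospitalization or its prolongation | No; an ER visit is not listed |
| Life-threatening | No; this needs an immediate risk of death when the event occurs, and potential threat is expressly excluded, so the Grade 4 label does not supply it |
| Important medical event | Only on medical judgment; the one mention of an emergency room is an example of bronchospasm needing intensive treatment, where the event and its treatment are the criterion and the visit is not |

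Under 8.3.4.1 the same event is recorded as an SAE with no further condition. The rules therefore differ for exactly one class: off the FDA scale, ER visit only, and not judged to be an important medical event. No section reconciles them.

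**How many events?** The documents give neither an ER-visit rate nor the share of events outside the FDA scale, so the number cannot be derived. To show scale only, let p be the proportion of participants with at least one such event, assumed to lie between 0.1% and 2%.

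- P(at least one affected participant) = 1 − (1 − p)^N
- Expected number affected = N × p
- N = 50 is the planned group size; N = 3 × 50 = 150 is groups 4E to 6E together (SAP Table 1)

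| p (assumed) | N = 50: P(≥1) | N = 150: P(≥1) | N = 150: expected |
|---|---|---|---|
| 0.1% | 4.9% | 13.9% | 0.15 |
| 0.5% | 22.2% | 52.9% | 0.75 |
| 1% | 39.5% | 77.9% | 1.5 |
| 2% | 63.6% | 95.2% | 3.0 |

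The N = 50 column reproduces the entries in Protocol Table 13 for these rates. That confirms the formula; Table 13 says nothing about ER visits.

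**Can the counts be separated later?** Table 60 lists each SAE with a reason, and the SAP's section 14.3.3 reserves a place for narratives in the study report. A reader could sort the events by hand if the reason field has an ER category or the narrative says so. The response options of that field are not in the documents. Tables 50 and 59 do not make the split.

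**The case against.** The best defence is that 8.3.2 is the section that defines SAEs, while 8.3.4.1 offers guidelines for describing severity. On that reading, its parenthesis is an instruction to record widely and send the event to the Medical Monitor. Section 8.3.2 also lets the sponsor as well as the investigator judge seriousness and has the sponsor review every SAE. Over-capture followed by review is a legitimate safety convention. The study tests no hypothesis, and each SAE is listed individually.

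Much of this stands: the rule is cautious and the effect on interpretation is small. What does not stand is that the text settles the matter. The parenthesis in 8.3.4.1 says the event is recorded as an SAE, not that it is reviewed for seriousness. Section 8.3.7.1 does not name the governing section, and nothing in the SAP says that reviewed events are reclassified before Tables 50 and 59 are made.

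A reader might also infer that ER-only events should lose SAE status altogether and that the related-SAE halting criterion in 7.1.1 should be narrowed to 8.3.2. The documents do not support going that far. After Day 28 following the last vaccination, Protocol 8.3.1 and 8.3.1.2 limit reporting to SAEs, special-interest events, MAAEs and new chronic conditions; 8.3.5, 9.4.4 and SAP section 9 set matching collection windows. MAAEs must be related. An unrelated ER-only event after Day 28 that fits no other category would then no longer be collected. Narrowing 7.1.1 would weaken a safety trigger, and it cannot affect 4E to 6E: each participant receives one study vaccination (SAP 9.2), and SAP 4.4.3 describes enrollment as past.

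**Conclusion.** The inconsistency is real and minor. For events outside the FDA scale, 8.3.4.1 has an ER visit alone recorded as an SAE, although 8.3.2 does not make it one and both 8.3.2 and 8.3.4 leave such cases to judgment. As a result, the SAE counts in SAP Tables 50 and 59 can include events that do not meet the protocol's own definition.

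It would be wrong to conclude that the counts are inflated. No document shows that any such event occurred, and an investigator may judge some ER-treated events to be important medical events, which are SAEs under either rule. The probabilities above rest wholly on the assumed 0.1% to 2%; that range is wide enough that it says only that zero is possible and so are a few. Nor is this a gap in safety reporting, since the rule captures more than 8.3.2 requires. The problem is one of labelling in the summary tables.

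**What to change.** Add one sentence to Protocol 8.3.4.1. It should say that a Grade 4 event involving an ER visit only is still handled as an SAE for reporting, collection and halting: SAE form within 24 hours, Medical Monitor review, and collection to the end of planned participation. It should add that the investigator records whether the event meets 8.3.2. The non-serious special-interest route in 8.3.9 is a precedent for using the SAE form while stating that the criteria are not met.

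In SAP Tables 50 and 59, count as SAEs the events that meet 8.3.2 and show ER-only Grade 4 events in a separate row. For 4E to 6E, make the split from the existing reason-for-SAE field in Table 60, or from the narrative if that field has no ER category.

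Leave the 7.1.1 halting criteria and all collection windows as they are. No safety trigger is weakened and no post-Day-28 data are lost. The cost is one extra investigator flag and a few table rows.

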8.3.4.2 Relationship to Study Intervention

For each reported adverse reaction, the participating site PI or qualified designee must assess the relationship of the event to the study product using the following guidelines:

Related – The AE is known to occur with the study intervention, there is a reasonable possibility that the study intervention caused the AE, or there is a temporal relationship between the study intervention and event. Reasonable possibility means that there is evidence to suggest a causal relationship between the study intervention and the AE.

Not Related – There is not a reasonable possibility that the administration of the study intervention caused the event, there is no temporal relationship between the study intervention and event onset, or an alternate etiology has been established.

Solicited adverse events reported in the 7 days after each vaccination are considered related to study product unless they are also recorded as an unsolicited event, in which case the relationship to study product will be determined by the PI or qualified designee.

8.3.5 Time Period and Frequency for Event Assessment and Follow-Up

For this study:

- solicited AEs will be collected for 7 days post each vaccination.
- unsolicited AEs will be collected until 28 days after each vaccination.
- SAEs, AESIs, MAAEs, and NOCMCs will be collected from Dose 1 to end of planned study participation.

